6.2 Toxicity Management

The management of specific AEs and laboratory parameters is described in the Operations Manual. This includes AEs of:

- Clinically significant (per investigator's discretion) dehydration due to diarrhea causing hospitalization, which is considered by the investigator or sponsor to be related to the study drug.
- Clinically significant (per investigator's discretion) electrolyte abnormalities due to diarrhea, which is considered by the investigator or sponsor to be related to the study drug.
- Clinically significant (per investigator's discretion) ECG abnormalities due to diarrhea, which is considered by the investigator or sponsor to be related to the study drug.

This also includes the following laboratory abnormalities: Significant electrolyte abnormalities related to diarrhea. For allowed study drug interruption, the following rules apply:

1. Allow study drug interruption up to 3 consecutive days for tolerability, AEs, and emergency surgery.
2. If the subject must undergo emergency surgery, the study drug should be interrupted at the time of the surgery. After emergency surgery, allow reintroduction of study drug once the physician has examined the surgical site and determined that it has healed and there is no sign of infection.
3. Additionally, the occurrence of intolerable diarrhea will be reported to the sponsor and will be monitored, in addition to all AE data, by an internal Dose Escalation Review Committee (open label cohorts Part 1) or an external DSMB (double-blind Part 2 [final cohort]), who, based on the frequency and severity of the events, could recommend halting the administration of investigational product.

7 STATISTICAL METHODS & DETERMINATION OF SAMPLE SIZE

7.1 Statistical and Analytical Plans

The statistical methods provided in this protocol will be focused on key analyses. Complete and specific details of the statistical analysis, including handling of missing data, will be described in the Statistical Analysis Plan (SAP).

7.2 Definition for Analysis Populations

The ITT Population includes all subjects who received at least 1 dose of study drug. The ITT Population will be used for all efficacy analyses.

The Safety Analysis Set consists of all subjects who received at least 1 dose of study drug.

7.3 Handling Potential Intercurrent Events for the Primary and Key Secondary Endpoints

The key efficacy endpoints (defined in Section 3.2) will be analyzed on the ITT population and subjects with the following potential intercurrent events will be handled as follows:

- The BMs for subjects who took a laxative, enema, or suppository on the calendar day of the BM or the calendar day before the BM will not be considered an SBM during the efficacy analysis.
- Subjects who discontinue prematurely during but prior to the completion of the study intervention period will have their eDiary data included up to the last dose date for the endpoint. The SBM frequency rate based on included eDiary data up to the last dose date will be considered equivalent to the 4-week SBM frequency rate.

- Subjects who have study drug interruption will have their eDiary data included as observed (i.e., regardless of interruption of study drug).

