3.2 Key Efficacy Endpoints and Estimand

Key efficacy endpoints for Part 1 and Part 2:

- Change from baseline in 4-week overall SBM frequency rate (SBMs/week) during the Study Intervention Period
- Change from baseline in 4-week stool consistency (Bristol Stool Form Scale) reported by a legally authorized representative (LAR)/parent/guardian/caregiver during the Study Intervention Period
- Change from baseline in 4-week straining reported by LAR/parent/guardian/caregiver during the Study Intervention Period

The estimands corresponding to the efficacy endpoint are the mean change from baseline in overall SBM frequency rate, stool consistency, and straining, regardless of premature discontinuation or interruption of study drug and without use of rescue medications in the linaclotide and placebo groups in the intent-to-treat (ITT) population.

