5.5 Withdrawal of Subjects and Discontinuation of Study

A subject whose LAR/parent/guardian gave consent may voluntarily withdraw the subject or the subject can be withdrawn from the study at any time for reasons including, but not limited to, the following:

- Clinically significant abnormal laboratory results or AEs, which rule out continuation of the study drug, as determined by the investigator or the Sponsor.
- The investigator believes it is in the best interest of the subject.
- The LAR/parent/guardian requests withdrawal from the study.
- Eligibility criteria violation was noted after the subject started study drug and continuation of the study drug would place the subject at risk.
- Introduction of prohibited medications or dosages and continuation of the study drug would place the subject at risk.
- The investigator determines the subject is significantly noncompliant with study procedures.

Discontinuation Criteria

A premature discontinuation will occur when a subject (whose LAR/parent/guardian who gave consent) ceases participation in the study, regardless of circumstances, before the completion of the protocol-defined study procedures.

Subjects **must be** prematurely discontinued from the study for reasons of safety including those who experience:

- An SAE considered by the investigator or the sponsor to be possibly related or related to study intervention,
- An AESI (Clinically significant [per investigator's discretion] dehydration due to diarrhea causing hospitalization, significant electrolyte abnormalities related to diarrhea and/or ECG abnormalities related to diarrhea that are considered by the investigator or sponsor to be related to the study drug. Refer to [Table 3](#) and [Table 4](#)),
- The presence of intentional overdose or intentional misuse per investigator discretion,
- The occurrence of any other AE that in the opinion of the investigator or the sponsor is possibly related or related to the study intervention that represents a clinically significant safety risk to the subject.

Table 3. Potentially Clinically Significant Electrolyte Values

Parameter	Lower Limit	Upper Limit
Bicarbonate	< 0.9 × LLN	> 1.1 × ULN
Chloride	< 0.9 × LLN	> 1.1 × ULN
Magnesium	< 0.9 × LLN	> 1.1 × ULN
Potassium	< 0.9 × LLN	> 1.1 × ULN
Sodium	< 0.9 × LLN	> 1.1 × ULN

LLN = lower limit of normal value provided by the laboratory; ULN = upper limit of normal value provided by the laboratory

Table 4. Potentially Clinically Significant ECG Values

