5.6 Follow-Up After Subject Discontinuation of Study Drug or from Study

To minimize missing data for efficacy and safety assessments, subjects who prematurely discontinue study drug treatment due to an AE should continue to be followed for all regularly scheduled visits, unless subject's LAR/parent/guardian has decided to discontinue the study participation entirely (withdrawal of informed consent). Subjects should be advised on the continued scientific importance of their data even if they discontinue treatment with study drug early.

If a subject prematurely discontinues study participation (withdrawal of informed consent), the procedures outlined for the Premature Discontinuation visit (PD visit) should be completed as soon as possible, preferably within 2 weeks of the last visit. In addition, if the LAR/parent/guardian is willing, the 1-week postintervention visit (after the last dose of study drug) may be completed to ensure all treatment-emergent AEs/SAEs have been resolved.

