3.0 Endpoints

3.1 Key Efficacy Endpoints for Part 1 and Part 2

The key efficacy endpoints for Part 1 and Part 2 are:

- The change from baseline in 4-week overall SBM frequency rate (SBMs/week) during the Study Intervention Period
- The change from baseline in 4-week stool consistency (Bristol Stool Form Scale) reported by LAR/parent/guardian/caregiver during the Study Intervention Period
- The change from baseline in 4-week straining reported by LAR/parent/guardian/caregiver during the Study Intervention Period

The details of the derivation of these efficacy endpoints are provided in [Appendix B](#).

The estimands corresponding to the efficacy endpoints are the mean change from baseline in overall SBM frequency rate, stool consistency, and straining during the study intervention period, regardless of interruption of study drug and without use of rescue medications in the linaclotide and placebo groups in the intent-to-treat (ITT) population.

3.2 Additional Efficacy Endpoints for Part 1 and Part 2

The additional efficacy endpoints for Part 1 and Part 2 are:

- The achievement of no longer meeting modified Rome IV criteria for FC at the end of the 4-week study intervention period
- The global change in symptoms at each week during the study intervention period
- The global severity of symptoms at each week during the study intervention period

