8.0 Handling of Potential Intercurrent Events for the Primary and Key Secondary Endpoints

The key efficacy endpoints (defined in Section 3.2) will be analyzed on the ITT population and subjects with the following potential intercurrent events will be handled as follows:

- The BMs for subjects who took a laxative, enema, or suppository on the calendar day of the BM or the calendar day before the BM will not be considered an SBM during the efficacy analysis.
- Subjects who discontinue prematurely during but prior to the completion of the study intervention period will have their eDiary data included up to the last dose date for the endpoint. The SBM frequency rate based on included eDiary

data up to the last dose date will be considered equivalent to the 4-week SBM frequency rate.

- Subjects who have study drug interruption will have their eDiary data included as observed (i.e., regardless of interruption of study drug).

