9.3.2 Main Analysis of Key Efficacy Endpoints

The estimands corresponding to the key efficacy endpoints are the mean change from baseline in overall SBM frequency rate, stool consistency, and straining, regardless of interruption of study drug and without use of rescue medications in the linaclotide and placebo groups in the intent-to-treat (ITT) population.

The key efficacy endpoints will be analyzed based on the AO approach. Descriptive statistics (mean, median, standard deviation, standard error, minimum, and maximum) will be provided.

The attributes of the estimand corresponding to the key efficacy objectives are summarized in [Table 1](#).

Table 1. Summary of the Estimand Attributes Corresponding to the Key Efficacy Objectives

Attributes of the Estimand					
Estimand Label	Treatment	Endpoint	Population	Handling of Intercurrent Events	Statistical Summary
Key	Part 1: linaclotide Part 2: linaclotide or placebo (see Section 3.1)	Change from baseline in 4-week overall SBM frequency rate (SBMs/week) during the study intervention period	ITT	IE1: use of any rescue therapy for the treatment of FC IE2: premature discontinuation of study drug IE3: study drug interruption due to poor tolerability All data occurred on the day of or the day after IE1 will not be used. All data after IE2 will not be used. All data after IE3 will be used.	Mean change from baseline in 4-week overall SBM frequency rate (SBMs/week) during the study intervention period in linaclotide (Part 1), or linaclotide or placebo (Part 2)
Key	Part 1: linaclotide Part 2: linaclotide or placebo (see Section 3.1)	Change from baseline in 4-week stool consistency (Bristol Stool Form Scale) reported by LAR/parent/guar dian/caregiver during the study intervention period	ITT	IE1: use of any rescue therapy for the treatment of FC IE2: premature discontinuation of study drug IE3: study drug interruption due to poor tolerability All data occurred on the day of or the day after IE1 will not be used. All data after IE2 will not be used. All data after IE3 will be used.	Mean change from baseline in 4-week stool consistency reported by LAR/parent/ guardian/ caregiver during the study intervention period in linaclotide (Part 1), or linaclotide or placebo (Part 2)

Attributes of the Estimand					
Estimand Label	Treatment	Endpoint	Population	Handling of Intercurrent Events	Statistical Summary

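### The key estimands in Protocol 3.2 apply whether or not study drug is stopped early, but the planned rules discard data after stopping, so the planned means are while-on-treatment means

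*Protocol*

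**What the plan says.** Protocol 3.2 gives one estimand sentence for SBM frequency, stool consistency and straining: the mean change from baseline "regardless of premature discontinuation or interruption of study drug and without use of rescue medications".

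Protocol 7.3 says that subjects who discontinue prematurely contribute diary data up to the last dose, and that the SBM rate from "eDiary data up to the last dose date will be considered equivalent to the 4-week SBM frequency rate". SAP 8.0 repeats the rule: "data up to the last dose date will be considered equivalent to the 4-week SBM frequency rate".

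SAP 9.3.2, Table 1, lists "IE2: premature discontinuation of study drug" in the row for each key endpoint, with the handling "All data after IE2 will not be used". Data after a drug interruption (IE3) are used.

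SAP 3.1 restates the estimand as "regardless of interruption of study drug and without use of rescue medications in the linaclotide and placebo groups". Discontinuation has gone from the sentence, and SAP 9.3.2 words it the same way. SAP 14.1, which should list changes from the protocol's analyses, has the entry NA.

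On follow-up, Protocol 5.6 says that "subjects who prematurely discontinue study drug treatment due to an AE should continue to be followed for all regularly scheduled visits", with the aim of limiting missing efficacy and safety data. Operations Manual Appendix A schedules the daily diary through the 1-week postintervention visit.

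**The concern.** An estimand that holds regardless of discontinuation calls for the subject's outcome over the whole 4 weeks, including the time after stopping. The rules instead take the on-drug rate, however short the record, as the 4-week rate. A programmer who follows the plan would report an answer to a different question from the one in Protocol 3.2. Diary entries made during the follow-up that Protocol 5.6 requires would be left out of the key summaries.

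No tests are planned, so the summary statistics are the whole efficacy result, and Protocol 4.1 says they will support the feasibility of a Phase 3 study. Groups are small: six per Part 1 cohort, and twelve randomized 1:1 in Part 2. One non-completer in six is within what the design allows. Protocol 4.1 asks for at least 5 completers per Part 1 cohort, and Protocol 5.5 does not replace subjects who stop.

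**Working it through.** **Text comparison**

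| Source | After study drug is stopped early | After study drug is interrupted |
|---|---|---|
| Protocol 3.2 | outcome counts regardless | outcome counts regardless |
| Protocol 7.3, SAP 8.0 | diary cut at last dose | data used as observed |
| SAP Table 1, three rows | data not used (IE2) | data used (IE3) |
| SAP 3.1 and 9.3.2, estimand sentence | not mentioned | outcome counts regardless |

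Interruption is handled consistently and discontinuation is not. The conflict lies inside the Protocol (3.2 against 7.3) and between Protocol 3.2 and the SAP.

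**Size**

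The documents give no SBM rates, effect size or dropout rate, so there is no stated figure to reproduce and every rate below is assumed.

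Inputs: a group of six (Protocol 4.1), a 28-day intervention period, and the enrollment/randomization day counted as half a day (SAP Appendix B). That convention is worded for the double-blind period; I apply it to Part 1 as well. The full period is then 27.5 days.

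For last dose on Day k, rate r_on to Day k and r_off afterwards, and baseline b:

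- planned rule: change = r_on − b
- Protocol 3.2 wording: change = [r_on × (k − 0.5) + r_off × (28 − k)] / 27.5 − b
- shift in a six-subject mean = (r_on − r_off) × (28 − k) / 27.5 / 6

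The shift does not depend on the baseline or on the other five subjects. To show whole means, I take b = 1 and the other five at +1.0.

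| r_on, r_off, k | Subject, planned rule | Subject, full period | Group means | Shift |
|---|---|---|---|---|
| 3, 2, Day 14 | +2.00 | 68.5/27.5 − 1 = +1.49 | 1.17 vs 1.08 | 0.08 |
| 4, 1, Day 7 | +3.00 | 47/27.5 − 1 = +0.71 | 1.33 vs 0.95 | 0.38 |
| 5, 1, Day 4 | +4.00 | 41.5/27.5 − 1 = +0.51 | 1.50 vs 0.92 | 0.58 |
| 5, 1, Day 3 | +4.00 | 37.5/27.5 − 1 = +0.36 | 1.50 vs 0.89 | 0.61 |
| 0, 1, Day 7 | −1.00 | 21/27.5 − 1 = −0.24 | 0.67 vs 0.79 | −0.13 |

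The first and fourth rows are the extremes for r_on 3 to 5, r_off 1 to 2 and k 3 to 14. The last row, outside that range, shows that the planned rule can also lower the mean. Counting Day 1 as a full day changes little: 14/28/6 = 0.083 in the first row and 4 × 24/28/6 = 0.571 in the third.

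The Table 1 cut also applies to the other two endpoints. For stool consistency, assume 4 SBMs of type 5 on drug, 3 of type 2 afterwards and a baseline of 2. The change is 5 − 2 = +3.00 under the rule and 26/7 − 2 = +1.71 over the period. The group mean shifts by 1.29/6 = 0.21 points.

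**The case against.** The strongest reply is that the analysis itself is clear. Protocol 7.3, SAP 8.0, Table 1 and both SAP estimand sentences fit one rule, and one phrase in Protocol 3.2 is out of line. While-on-treatment is a legitimate strategy, Protocol 7.1 leaves full detail to the SAP, and no test or powered sample size depends on the choice. This stands as an argument about severity and as support for the smaller edit. It does not remove the conflict: Protocol 7.3 disagrees with 3.2 inside the same document. The SAP also predates the current protocol, so its NA entry may reflect age, but the two texts still disagree.

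Two readings might reconcile the text. The first is that the Protocol 3.2 wording only keeps discontinuers in the analysis set. That fails because the same phrase covers interruption, for which later data are used. The second is that Protocol 7.3 means study leavers, since Protocol 5.5 defines premature discontinuation as when a subject "ceases participation in the study, regardless of circumstances, before the completion of the protocol-defined study procedures". That is possible for 7.3, but Table 1 names study drug.

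It is also fair that few subjects can be affected. Protocol 5.6 promises continued visits only after AE-related drug stops, and Protocol 5.5 takes some subjects out of the study altogether. Continued diary entry after stopping is inferred from the general schedule and is not stated for discontinuers. For a subject with no later diary, both definitions fall back on the on-drug rate.

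Three stronger inferences are not supported:

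- *That the chance of such a stop can be estimated.* A reader might compute 1 − 0.988^6 = 7% from the 1.2% in LIN-MD-64, or 40% from none in 35 in LIN-MD-67 (one-sided upper 95% bound 1 − 0.05^(1/35) = 8.2%, then 1 − 0.918^6). LIN-MD-64 ran 12 weeks in older children. The 35 include placebo subjects, and the 40% is a value at a confidence bound, not an estimate. Both count AE stops, whether or not a diary continued.
- *That the median protects the result.* It stays at +1.0 in the table only because the other five subjects are all set there.
- *That every early discontinuation distorts the mean.* Only stops followed by diary data can make the two definitions differ.

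**Conclusion.** The point holds as a mismatch between the stated estimand and the planned analysis. The planned means for all three key endpoints are while-on-treatment with respect to discontinuation, Protocol 3.2 says otherwise, and SAP 14.1 does not declare the difference. The text alone establishes this.

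The numerical effect is conditional. It needs a subject who stops drug, remains in the study, keeps a diary and has a different rate afterwards. Under the assumed rates, one such subject in six shifts the SBM mean by about 0.1 to 0.6 per week. If there is none, the reported means are unaffected. The study is descriptive and the harm limited, but the choice should be settled before results are known.

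**What to change.** Adopt one strategy in both documents.

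**(a) Keep Protocol 3.2.** Use all available diary data to the end of the 4-week period regardless of study-drug discontinuation, with diary days contributed as the denominator. In Protocol 7.3 and SAP 8.0, delete the last-dose cut and the sentence equating the on-drug rate with the 4-week rate. Delete the IE2 data exclusion from the three rows of Table 1. Restore premature discontinuation in the SAP 3.1 and 9.3.2 estimand sentences. Keep the on-drug rate as a supportive summary, and state that subjects with no later diary keep their on-drug rate. This option makes use of the follow-up in Protocol 5.6.

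**(b) Keep the rule; the smaller edit.** Remove premature discontinuation from Protocol 3.2, label the strategy while-on-treatment, and report the full-period rate from available diary data as a sensitivity summary. SAP 14.1 needs an entry only if Protocol 3.2 is left as it is.

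Under either option, say in Protocol 7.3 whether discontinuing prematurely means stopping study drug or leaving the study.

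The cost is wording plus a supportive or sensitivity table from a diary already scheduled. The protocol change needs IEC/IRB approval (Protocol 8.1). The main drawback is that data after stopping may be incomplete, chiefly for stops not caused by an AE.

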7.4 Statistical Analyses for Efficacy

The efficacy analysis will be summarized in the ITT Population descriptively and no statistical testing will be performed in this study.

Summary and Analysis of the Key Efficacy Endpoints

Analysis of the key efficacy endpoints will be conducted on the ITT population. The key efficacy endpoints will be analyzed via descriptive summary statistics in terms of mean, median, standard deviation, standard error of mean, minimum, and maximum.

The numerator of the SBM rate (SBMs/week) during the Study Intervention Period will be derived based on the total number of SBMs reported by a LAR/parent/guardian/caregiver as being directly observed during this period in the eDiary. Additional analysis will also be performed based on the total number of SBMs reported during the Study Intervention Period (including SBMs not directly observed by the LAR/parent/guardian/caregiver) and the corresponding baseline SBM frequency rate will be determined based on the total number of SBMs reported during the Preintervention period.

Stool consistency for each LAR/parent/guardian/caregiver-observed BM will be measured daily in the eDiary using the 7-point ordinal BSFS. A participant's BSFS score for the Study Intervention Period will be the average of the non-missing BSFS scores from the caregiver-observed SBMs during the 4-week Study Intervention Period. If no caregiver-observed SBMs are present at baseline, the baseline BSFS score reported by the caregiver will be missing and, therefore, that subject will not be included in the change from baseline stool consistency analysis.

Straining for each LAR/parent/guardian/caregiver caregiver-observed BM will be collected daily in the eDiary device, using a 4-point scale based on two questions. The subject's average straining score for each caregiver-observed BM will be derived based on the average of nonmissing responses of the two straining questions. The participant's straining score in the 4-week Study Intervention Period will be the average of the non-missing average straining scores from all caregiver-observed SBMs during the 4-week Study Intervention Period. If a subject has no caregiver-observed SBMs at baseline, then the baseline straining score reported by the caregiver will be missing and, therefore, that subject will not be included in the change from baseline straining analysis.

Subgroup Analysis for Efficacy

The key efficacy endpoints will be summarized descriptively for age groups from 6-months to less than 1 year and 1 year to 2 years of age.

